- 10. Participant has experienced any of the following within 6 months (24 weeks) of signing informed consent/assent: clinically significant cardiac disease, myocardial infarction, severe/unstable angina, coronary/peripheral artery bypass graft, cerebrovascular accident, transient ischemic attack, or symptomatic pulmonary embolism;
- 11. Participant has recorded a LVEF < 55% at Screening or within 3 years of signing informed consent/assent, OR has a history of congestive heart failure;
- 12. Participant has a history of, or evidence of, retinal pathology on ophthalmologic examination that is considered a risk factor for central serous retinopathy, retinal vein occlusion (RVO), or neovascular macular degeneration. Participants will be excluded from study participation if they have any of the following risk factors for RVO at Screening:

- 12.1. Intraocular pressure > 21 mmHg;
- 12.2. Serum cholesterol > 300 mg/dL;
- 12.3. Serum triglycerides > 300 mg/dL;
- 12.4. Hyperglycemia (fasting blood glucose > 125 mg/dL or random blood glucose > 200 mg/dL);
- 12.5. Age specific hypertension
 - 12.5.1. Participants \geq 13 years of age with a blood pressure \geq 140/90 mm Hg
 - 12.5.2. Participants \leq 12 years of age with a blood pressure \geq 95th percentile for age +12 mmHg (Section 10.11);
- 13. Participant has a history of glaucoma;
- 14. Participant has a history of a positive human immunodeficiency virus (HIV) antibody test;
- 15. Participant has a known malabsorption syndrome or preexisting gastrointestinal conditions that may impair absorption of PD-0325901 (e.g., gastric bypass, lap band, or other gastric procedures). Delivery of PD-0325901 via nasogastric tube or gastrostomy tube is not allowed;

Prior/Concomitant Therapy

- 16. Participant has received NF1 PN-targeted therapy (e.g., farnesyltransferase inhibitors, kinase inhibitors, etc.) within 45 days of first dose of study treatment (or 5.5 half-lives, whichever is longer). All toxicities from prior therapy must resolve to ≤ Grade 1 or Baseline;
- 17. Participant previously received or is currently receiving therapy with PD-0325901 or any other MEK1/2 inhibitor (e.g., selumetinib, trametinib, cobimetinib, binimetinib, etc.);

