6.6. Dose Modification

Every effort should be made to administer study treatment at 2 mg/m² BID; however, in the event of significant toxicity, dosing must be interrupted and/or dose reduced as described in Table 4 and Table 5.

Interruption of study treatment should continue until the toxicity is resolved to \leq Grade 1 or Baseline. An interruption of study treatment for more than 14 days due to any toxicity may require permanent discontinuation. After 14 days of interruption, study treatment may be resumed only after discussion with the Medical Monitor and approval by the Sponsor. Refer to Section 10.10.3 for the Medical Monitor contact details.

After interruption, study treatment may be resumed at a reduced dose as described in Table 4 and Table 5. Should the same Grade toxicity recur at the reduced dose and the AE is considered related to the study treatment, the participant may be discontinued at the discretion of the Investigator, pursuant to discussion with the Medical Monitor and Sponsor. Following a dose reduction, an increase in the study treatment dose due to a BSA change is permitted at the discretion of the Investigator with approval from the Medical Monitor and Sponsor.

An unscheduled visit may be performed at any time during the study. Assessments to be performed at the visit will be determined by the Investigator.

Table 4 Criteria For Dose Modification For Study Drug Related Adverse Events

RELATED ADVERSE EVENTS	INTERVENTION
OCULAR/VISUAL	
Any Grade ≤ 2 event.	Continue dosing and perform ophthalmologic exams every 2 to 4 weeks until resolution to Grade ≤ 1 or baseline.
Any Grade ≥ 3 event except RVO.	Interrupt dosing; if resolution to Grade ≤ 1 or baseline occurs within 14 days, re-start study treatment at the next lower dose following Table 5. Consider ophthalmologic exams every 2 to 4 weeks.
Grade ≥ 3 retinal vein occlusion (RVO)	Permanently discontinue study treatment
NEUROLOGICAL	
Grade ≤ 2 events such as hallucination, confusion or delirium lasting more than 24 hours AND after ruling out other possible causes.	Interrupt dosing; if resolution to Grade ≤ 1 or baseline occurs within 14 days, re-start study treatment at the next lower dose following Table 5.
Any Grade ≥ 3 event.	Withhold dose and discuss with the Medical Monitor. Consider permanent discontinuation after re-evaluating the benefit risk of ongoing study drug treatment
MUSCULOSKELETAL	

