Grade \geq 3 muscle weakness (symptomatic and interfering with ADL).	Interrupt dosing; if resolution to Grade ≤ 1 or baseline occurs within 14 days, re-start study treatment at the next lower dose following Table 5.
DERMATOLOGICAL	
Grade ≥ 3 acneiform rash.	Interrupt dosing; if resolution to Grade ≤ 1 or baseline occurs within 14 days, restart study treatment at the next lower dose following Table 5.
CARDIAC	
Asymptomatic, absolute decrease in left ventricular ejection fraction (LVEF) of \leq 10% from baseline and is below institutional lower limit of normal (LLN).	Interrupt dosing; if LVEF value improves to above the institutional LLN or baseline, resume at the same dose, if supported by the investigator's assessment of the benefit-risk ratio.
	If LVEF does not improve to above the institutional LLN or baseline within 14 days, permanently discontinue study treatment.

Asymptomatic, absolute reduction in LVEF of $> 10\%$ to $\le 19\%$ from baseline and is below institutional lower limit of normal (LLN).	Interrupt dosing; if LVEF value improves to above the institutional LLN or baseline within 14 days, resume at the next lower dose level following Table 5. If LVEF does not improve to above the institutional LLN or baseline within 14 days, permanently discontinue study treatment.
Symptomatic congestive heart failure. Absolute decrease in LVEF of greater than 20% from baseline.	Permanently discontinue study treatment.
LIVER (Refer to Section 7.1.1)	
OTHER	
Grade \geq 3 hematologic toxicities or clinically significant Grade 2 hematologic abnormalities, that do not resolve within 72 hours after initiation of medical management.	Interrupt dosing; if resolution to Grade ≤ 1 occurs within 14 days, restart study treatment at the next lower dose following Table 5.
Grade ≥ 3 nonhematologic toxicity that is not controlled by optimal supportive medication.	Interrupt dosing; if resolution to Grade ≤ 1 or baseline occurs within 14 days, restart study treatment at the next lower dose following Table 5.
Other Grade 2 toxicity that is subjectively intolerable (except alopecia) and not controlled by optimal supportive medication.	Interrupt dosing; if resolution to Grade ≤ 1 or baseline occurs within 14 days, re-start study treatment at the same dose.

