10.1.7. Study and Site Closure

The Sponsor reserves the right to suspend or terminate the study at any time for any reason at the sole discretion of the Sponsor. Reasons which would cause the Sponsor to suspend/terminate enrollment include, but are not limited to, the occurrence of any of the following:

- One Grade 5 AE;
- Two Grade 4 AEs;
- One occurrence of any of the following ocular toxicities: retinal vein occlusion, unexplained Grade 3+ Optic Neuropathy, Grade 3+ retinal vein detachment, or unexplained Grade 3+ retinopathy;
- Two absolute decreases in LVEF > 20% from Baseline of the Treatment Phase or symptomatic congestive heart failure not explained by any other cause; or
- One participant meeting QTc stopping criteria as described in Section 7.1.2.

Study Sites will be closed upon study completion. A study Site is considered closed when all required documents and study supplies have been collected, a study Site closure visit has been performed, and the IRB has been notified of closure.

Study Site closure prior to completion of the study should be avoided. The Investigator and Sponsor will agree to the circumstances that could cause early study Site closure.

The Sponsor reserves the right to close the study Site at any time for any reason at the sole discretion of the Sponsor. Reasons for the early closure of a study Site by the Sponsor or Investigator may include but are not limited to:

- Failure of the Investigator to comply with the protocol, the requirements of the IRB/IEC or local health authorities, the Sponsor's procedures, or GCP guidelines;
- Inadequate recruitment of participants by the Investigator; or
- Discontinuation of further study treatment development.

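### For study-drug-related events, Table 4 has no cardiac row for an asymptomatic, below-LLN fall in LVEF of more than 19 and up to 20 points

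*Protocol*

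**What the plan says.** Protocol 6.6 makes the table binding for significant toxicity: "dosing must be interrupted and/or dose reduced as described in Table 4 and Table 5". By its title, Table 4 applies to adverse events related to study drug. Its cardiac section has three rows:

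- **Row 1:** asymptomatic, absolute fall of at most 10%, LVEF below LLN. Interrupt, and resume at the same dose on recovery.
- **Row 2:** asymptomatic, absolute fall above 10% and up to 19%, LVEF below LLN. Interrupt, and if LVEF "improves to above the institutional LLN or baseline within 14 days, resume at the next lower dose level following Table 5".
- **Row 3:** symptomatic congestive heart failure, or "Absolute decrease in LVEF of greater than 20% from baseline". Permanent discontinuation, with no LLN condition.

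Rows 1 and 2 share a hard stop: "If LVEF does not improve to above the institutional LLN or baseline within 14 days, permanently discontinue study treatment".

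Outside the cardiac rows, the table's OTHER section has a row for a Grade 3 or higher "nonhematologic toxicity that is not controlled by optimal supportive medication". It requires interruption and a restart at the next lower dose if the event resolves to Grade 1 or baseline within 14 days. The general text of 6.6 asks that an interruption last until the toxicity is back to Grade 1 or baseline. It treats permanent discontinuation after more than 14 days as possible rather than required, and adds: "After 14 days of interruption, study treatment may be resumed only after discussion with the Medical Monitor and approval by the Sponsor".

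The study-level suspension criteria in 10.1.7 use the same cut-off as row 3: "Two absolute decreases in LVEF > 20% from Baseline of the Treatment Phase".

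**The concern.** Rows 1 and 2 meet exactly at 10 points, so the table appears meant to be continuous. Rows 2 and 3 do not meet: one ends at 19 inclusive and the other starts strictly above 20. The size of the fall should order the response, yet a 20-point fall carries a weaker written rule than a 19-point fall. At stake is one safety provision, the mandatory permanent stop for a participant whose LVEF has not recovered by day 14. No clinical reason for treating this band differently is given. Section 10.1.7 does not close the gap, because it is also strictly above 20 and concerns suspension of the study or enrollment, not the individual's dose.

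**Working it through.** The plan states no figure to reproduce. The check is whether the three ranges cover every fall, and whether an uncovered fall can occur.

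**Inputs.** Row limits from Table 4. Entry floor of 55% from exclusion criterion 11 (5.2): "Participant has recorded a LVEF < 55% at Screening or within 3 years of signing informed consent/assent". The screening echocardiogram serves as baseline (Treatment Phase schedule, footnote 16a). The documents give no LLN value, only the institutional one, so 50%, 53% and 55% are assumptions.

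**Step 1: coverage.** Let d = baseline LVEF − current LVEF, in points, for an asymptomatic participant now below LLN. The rows cover d ≤ 10, 10 < d ≤ 19, and d > 20. What remains is 19 < d ≤ 20.

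| d | Row |
|---|---|
| 10 | 1 |
| 10.5 | 2 |
| 19 | 2 |
| 19.1, 19.5, 19.9, 20 | none |
| 20.1 | 3 |
| 21 | 3 |

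In whole points from 1 to 40, the only uncovered value is 20. If sites report to 0.1 point (an assumption; 8.2.8 fixes no precision), ten values are uncovered, 19.1 to 20.0.

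**Step 2: can it occur?** A 20-point fall ends below LLN when baseline − 20 < LLN, that is, baseline < LLN + 20. With baseline at least 55, in whole percent:

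- LLN 50%: baselines 55 to 69
- LLN 53%: baselines 55 to 72
- LLN 55%: baselines 55 to 74

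The case is therefore open to a wide range of eligible baselines.

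**Step 3: what each neighbour requires.** Take a baseline of 60%, with every result below any of the assumed LLNs:

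| LVEF now | Fall | Cardiac row | Cardiac rule | If not recovered by day 14 |
|---|---|---|---|---|
| 41% | 60 − 41 = 19 | 2 | interrupt | permanent stop, mandatory |
| 40% | 60 − 40 = 20 | none | none | no mandatory stop |
| 39% | 60 − 39 = 21 | 3 | permanent stop at once | not applicable |

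**Step 4: what the fallbacks supply at 20 points.** If the OTHER row applies, its first steps (interrupt, then restart one dose level lower on recovery) match row 2, but it has no day-14 permanent stop. Whether it applies depends on the CTCAE grade of the fall and on control by supportive medication; the documents do not give the grade. The general 6.6 text supplies a hold until recovery and a gated restart, again without a mandatory stop. Section 7.1 leaves discontinuation to Investigator judgement. Section 8.3.1 requires reporting of decreased ejection fraction within 24 hours at Grade 2 or above and encourages contact with the Medical Monitor, but sets no dosing action.

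**The case against.** The strongest reply is that nobody would be harmed by this wording. A site that holds dosing for falls of 1 to 19 points below LLN, and stops for 21, would hardly keep dosing at 20. Once dosing is held, 6.6 says that it should stay held until the toxicity is back to Grade 1 or baseline, and a restart after 14 days needs both the Medical Monitor and the Sponsor. Prompt reporting and Investigator discretion come on top.

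Much of this stands, and it rules out several stronger readings that a reader might infer:

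- **That a participant with an unrecovered 20-point fall may simply be re-dosed.** The hold-until-resolved sentence in 6.6 speaks against it. What is lost is row 2's permanent stop at day 14; what remains is a hold with a gated restart.
- **That every 19-point fall must be stopped if unrecovered.** This holds only for study-drug-related events, asymptomatic and below LLN.
- **That the OTHER row's recovery test is looser than row 2's.** The documents do not give the CTCAE grading of an LVEF fall, so the two tests cannot be ranked from the text.
- **That smaller falls or heart failure are also uncovered.** Falls of up to 19 points that stay at or above LLN are left out of rows 1 and 2 by their own condition, and symptomatic heart failure is in row 3 at any size of fall.

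The reply does not supply a cardiac-specific instruction for 20 points or restore the mandatory day-14 stop. Good sense at the site may fill the gap, but the table is meant to give the instruction itself.

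**Conclusion.** The gap is real and narrow. For study-drug-related events, an asymptomatic, below-LLN fall above 19 and up to 20 points has no cardiac row, and with whole-percent reporting this is the single value 20. The size of the gap rests on the text alone; only the range of baselines at which it can arise depends on an assumed LLN. The consequence is the absence of a cardiac-specific interruption rule and of the mandatory day-14 stop, with the general safeguards still in place.

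The documents give no frequency of LVEF falls of this size, so the number of participants affected cannot be estimated; it is probably small. No endpoint, analysis set or sample size is touched. Severity is minor, and confidence in the gap itself is high.

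**What to change.** Make rows 2 and 3 meet, keeping row 2's asymptomatic and below-LLN conditions. There are two ways:

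- **Least change:** row 2 becomes > 10% to ≤ 20%. Row 3 and 10.1.7 stay at > 20% and remain aligned. This is one number in Table 4. The ranges are then d ≤ 10, 10 < d ≤ 20 and d > 20, with nothing left over.
- **More cautious:** row 2 becomes > 10% to < 20% and row 3 becomes ≥ 20%. Both edits are needed, plus a third in 10.1.7 if the sponsor wants the cut-offs to agree. The ranges are then d ≤ 10, 10 < d < 20 and d ≥ 20, again complete. The cost is that a participant with exactly a 20-point fall loses the option to resume. Because row 3 carries no LLN condition, this would include someone still at LLN (for example, 75 − 20 = 55 with an LLN of 55%).

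The choice is a clinical one for the sponsor. Row 2's present end at 19 may hint that the upper band was meant to start at 20, but the written cut-offs in row 3 and 10.1.7 both say above 20. Either version needs only a wording change in the protocol and no statistical rework.

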6.7. Treatment after the End of the Study

Long-Term Follow-up Phase:

Participants who complete Cycle 24 of the Treatment Phase and did not meet withdrawal criteria (Section 7) are eligible to participate in the LTFU Phase. Eligible participants will continue taking the last dose assigned in the Treatment Phase (approximately 2 mg/m² BID [maximum dose of 4mg BID]) of PD-0325901 (mirdametinib; open-label study treatment), on an intermittent (3 weeks on/1 week off) dosing schedule in 28-day cycles. Participants will remain in the LTFU Phase until a withdrawal criterion is met as described in Section 7 or mirdametinib is commercially available.

7. Discontinuation of Study Treatment and Participant Discontinuation/Withdrawal

7.1. Discontinuation of Study Treatment

It may be necessary for a participant to permanently discontinue study treatment prematurely or for the Sponsor to suspend study enrollment.

Participants who permanently discontinue from the Treatment Phase prior to the Cycle 24 visit will be required to return to the clinic for an early termination (ET) visit as close as possible to the last dose of study treatment (PD-0325901, mirdametinib). Participant will also be required to return for a Safety Follow-Up visit (30 days [+5 days] after the last dose of study drug) (refer to the SoA in Section 1.3 for timing and a complete list of required assessments to be conducted).

Conditions upon which the Sponsor will suspend additional enrollment in the study are described in the specified stopping criteria in Section 10.1.7.

Reasons for discontinuation of study treatment early may include:

[figure not shown]
- Participants who meet the definition of progressive disease (a ≥ 20% increase in the volume of the target PN as compared to the Treatment Phase Baseline [Section 10.7], confirmed by central radiologic review);
- Occurrence of any medical condition or circumstance that exposes the participant to substantial risk and/or does not allow the participant to adhere to the requirements of the protocol.
- Any SAE (refer to Section 10.3.2 for SAE criteria), clinically significant AE (refer to QTc stopping criteria below; Section 7.1.2), severe laboratory abnormality (refer to liver chemistry stopping criteria below; Section 7.1.1), intercurrent illness, RVO, or other medical condition which indicates to the Investigator that continued participation is not in the best interest of the participant;
- Pregnancy (refer to Sections 8.3.6 and 10.4 for additional details);
- Requirement of prohibited concomitant medication (Section 6.5.2);
- Participant failure to comply with protocol requirements or study-related procedures; or
- Termination of the study by the Sponsor as described in Section 10.1.7, the IRB or the regulatory authority.

7.1.1. Liver Chemistry Stopping Criteria

Discontinuation of study treatment for abnormal liver function should be considered by the Investigator when a participant meets one of the conditions outlined in Figure 1 or if the Investigator believes that it is in the best interest of the participant.

Figure 1 Liver Chemistry Stopping Criteria and Increased Monitoring Algorithm

➤ If participant is to be monitored weekly, must refer to Liver Safety: Suggested Actions and Follow-up Assessments (Section 10.5)

Abbreviations: ALT = alanine transaminase; INR = international normalized ratio; SAE = serious adverse event; ULN = upper limit of normal.

- ➤ Must refer to Liver Safety: Suggested Actions and Follow-up Assessments (Section 10.5)
- **Report as an SAE if possible Hy's Law case:** ALT \geq 3xULN and Bilirubin \geq 2xULN (> 35% direct) or INR > 1.5, if measured*
 - *INR value not applicable to participants on anticoagulants

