HGB HCT PLT count RBC count RBC Indices: MCV MCH MCH MBCC with Differential ¹ : In neutrophils Imphocytes monocytes eosinophils basophils	 AST/SGOT ALT/SGPT Total and Direct BIL GGT Sodium Chloride Potassium Calcium Bicarbonate Inorganic phosphorus Alkaline phosphatase Creatinine³ Creatine Kinase BUN Glucose (non-fasting) Uric acid Albumin Total protein Triglycerides Total Cholesterol 	 Specific gravity Bilirubin Glucose Leukocyte esterase Nitrite Protein Urobilinogen Blood Ketones pH Microscopy⁴ 	HBV HBsAg HCV hepatitis C antibody (HCV PCR if hepatitis C antibody positive)

ALT = alanine aminotransferase; AST = aspartate aminotransferase; BIL = bilirubin; BUN = blood urea nitrogen; GGT = gamma-glutamyl transferase; HBsAg = hepatitis B surface antigen; HBV = hepatitis B virus; HCT = hematocrit; HCV = hepatitis C virus; HGB = hemoglobin; MCH = mean cell hemoglobin; MCV = mean cell volume; PCR = polymerase chain reaction; PLT = platelet; RBC = red blood cell; SGOT = serum glutamic-oxaloacetic transaminase; SGPT = serum glutamic-pyruvic transaminase; WBCC = white blood cell count

- 1. Manual microscopic review is performed only if white blood cell count and/or differential values are out of reference range.
- 2. Details of liver stopping criteria and required actions and follow-up assessments after liver stopping or monitoring event are given in Sections 7.1.1 and 10.5.
- 3. Creatinine < the maximum age specific serum creatinine seen below, or calculated creatinine clearance ≥ 60 mL/min (using the Cockcroft-Gault formula).

Age (years)	Maximum Serum Creatinine (mg/dL)
≤5	0.8
> 5 and ≤ 10	1.0
> 10 and ≤ 15	1.2
> 15	1.5

- Microscopy examination is performed only if blood or protein is abnormal.
- Serology only required at Screening.

10.3. Appendix 3: Adverse Events: Definitions and Procedures for Recording, Evaluating, Follow-up, and Reporting

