- Repeat liver chemistry tests (include ALT, AST, alkaline phosphatase, bilirubin and INR) and perform liver chemistry follow-up assessments within 24 to 72 hours.
- Monitor participants weekly until liver chemistry abnormalities resolve, stabilize, or return to baseline.

If ALT \geq 3 x ULN AND bilirubin \geq 2 x ULN or INR > 1.5:

- Anti-nuclear antibody, anti-smooth muscle antibody, Type 1 anti-liver kidney microsomal antibodies, and quantitative total IgG or gamma globulins.
- Serum acetaminophen adduct HPLC assay (quantifies potential acetaminophen contribution to liver injury in participants with definite or likely acetaminophen use in the preceding week [James, 2009]).
- Liver imaging (ultrasound, magnetic resonance, or computerized tomography) and/or liver biopsy to evaluate liver disease; complete liver.

AE = adverse event; ALT = alanine aminotransferase; AST = aspartate aminotransferase; CPK = creatine phosphokinase; eCRF = electronic case report form; HPLC = high performance liquid chromatography; IgG = immunoglobulin G; INR = international normalized ratio; LDH = lactate dehydrogenase; SAE = serious adverse event; ULN = upper limit of normal

- Serum bilirubin fractionation should be performed if testing is available. If serum bilirubin fractionation is not immediately available, discontinue study treatment if ALT ≥ 3 x ULN and bilirubin ≥ 2 x ULN. Additionally, if serum bilirubin fractionation testing is unavailable, record the absence/presence of detectable urinary bilirubin on dipstick which is indicative of direct bilirubin elevations suggesting liver injury.
- All events of ALT ≥ 3 x ULN and bilirubin ≥ 2 x ULN (> 35% direct bilirubin) or ALT ≥ 3 x ULN and INR > 1.5 may indicate severe liver injury (possible 'Hy's Law') and must be reported as an SAE (excluding studies of hepatic impairment or cirrhosis). The INR stated threshold value will not apply to participants receiving anticoagulants.
- 3. New or worsening symptoms believed to be related to liver injury (such as fatigue, nausea, vomiting, right upper quadrant pain or tenderness, or jaundice) or hypersensitivity (such as fever, rash or eosinophilia).
- 4. Includes: Hepatitis A immunoglobulin M (IgM) antibody; hepatitis B surface antigen and hepatitis B core antibody; hepatitis C RNA; cytomegalovirus IgM antibody; Epstein-Barr viral capsid antigen IgM antibody (or if unavailable, heterophile antibody or monospot testing); and hepatitis E IgM antibody.

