Liver Chemistry Increased Monitoring Criteria with Continued Study Treatment

Liver Chemistry Increased Monitoring Criterion and Follow-Up		
Criterion		Actions
Criterion ALT ≥ 3 x ULN and < 5 x ULN and bilirubin < 2 x ULN, without symptoms believed to be related to liver injury or hypersensitivity, and participant can be monitored weekly for 4 weeks	•	Notify the Medical Monitor within 24 hours of learning of the abnormality to discuss participant safety. Participant can continue study treatment Participant must return weekly for repeat liver chemistry tests (ALT, AST, alkaline phosphatase, bilirubin) until the abnormalities resolve, stabilize or return to baseline. If at any time, the participant meets liver chemistry stopping criteria, proceed as described
	•	in Section 7.1.1. If, after 4 weeks of monitoring, ALT < 3 x ULN and bilirubin < 2 x ULN, monitor participant twice monthly until liver chemistry tests resolve, stabilize, or return to baseline.

References

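### Protocol 7.1.1 leaves stopping for a possible Hy's Law case to the investigator's consideration, while Appendix 5 treats the same event as a stop

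*Protocol*

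**What the plan says.** **Section 7.1.1, lead sentence.** "Discontinuation of study treatment for abnormal liver function should be considered by the Investigator" when a participant meets a Figure 1 condition, or when the investigator thinks stopping is in the participant's best interest.

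**Section 7.1.1, text around Figure 1.** The reader is sent to Appendix 5 twice. One reference, tied to weekly monitoring, reads "must refer to Liver Safety: Suggested Actions and Follow-up Assessments (Section 10.5". The other has no such condition and stands just above the instruction to report a possible Hy's Law case as an SAE. That case is ALT ≥ 3 × ULN with either bilirubin ≥ 2 × ULN (> 35% direct) or INR > 1.5, with INR not applied to participants on anticoagulants.

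**Appendix 5 (Section 10.5).** The same ALT and bilirubin combination is one of six entries under the stopping-criteria heading. Footnote 1 says: "If serum bilirubin fractionation is not immediately available, discontinue study treatment if ALT ≥ 3 x ULN and bilirubin ≥ 2 x ULN". Footnote 2 describes the bilirubin and INR combinations as possibly indicating severe liver injury "and must be reported as an SAE (excluding studies of hepatic impairment or cirrhosis"). The table for increased monitoring with continued treatment is limited to "ALT ≥ 3 x ULN and < 5 x ULN and bilirubin < 2 x ULN", with further conditions on symptoms and weekly monitoring. It adds "If at any time, the participant meets liver chemistry stopping criteria, proceed as described" in Section 7.1.1.

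**Other places.** The liver row of Table 4 (Section 6.6) has no rule of its own and points to 7.1.1. Table 11, footnote 2 (Section 10.2) says: "Details of liver stopping criteria and required actions and follow-up assessments after liver stopping or monitoring event are given in Sections 7.1.1 and 10.5".

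**The concern.** ALT and bilirubin rising together past these limits is the liver event the protocol itself marks as most serious. It is also the event for which the investigator most needs one clear instruction, because the decision to hold or stop may have to be made the same day. Section 7.1.1 is where Table 4 and the monitoring table send the investigator for that instruction. Its governing sentence asks only that stopping be considered. Appendix 5 reads as though the decision has already been made.

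Two sites could therefore handle the same laboratory result differently, each citing the protocol. The trial enrols children from age 2, treats for up to 24 cycles, and then offers open-ended treatment in the Long-Term Follow-up Phase. Uneven handling would matter first for participant safety. It would also make discontinuations for liver events harder to interpret.

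**Working it through.** No arithmetic applies. The check sets the texts side by side and asks whether they give the same event the same force.

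**1. Are the thresholds the same?** Yes. Both 7.1.1 and Appendix 5 use ALT ≥ 3 × ULN with bilirubin ≥ 2 × ULN (> 35% direct), or with INR > 1.5. Any conflict concerns the action only.

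**2. What action does each text attach to the bilirubin combination?**

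| Place | Action in the readable text | Force |
|---|---|---|
| 7.1.1, lead sentence | consider stopping | discretionary |
| 7.1.1, Hy's Law line | report as SAE; consult Appendix 5 | mandatory, but silent on stopping |
| Appendix 5, criteria list | listed as a stopping criterion | a stop by its heading |
| Appendix 5, footnote 1 | discontinue, if fractionation is not immediately available | mandatory |
| Appendix 5, monitoring table | dosing may continue only if bilirubin < 2 × ULN | no continuation route at ≥ 2 × ULN |

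Footnote 1 deals with a participant whose direct fraction is not yet known. Telling the investigator to stop in that case makes sense only if meeting the full criterion also means stopping. The monitoring table agrees, since it covers no participant at or above 2 × ULN bilirubin.

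**3. Do the cross-references settle it?** No. 7.1.1 sends the reader to Appendix 5, and Appendix 5 sends a participant who meets the criteria back to 7.1.1. Table 4 points to 7.1.1 only. Neither section is said to prevail.

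**4. Do the labels settle it?** No. The title of Appendix 5, repeated in 7.1.1, calls the actions suggested. Table 11, footnote 2 calls the actions in those same two sections required.

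**5. How does the protocol word a stop it means to be mandatory?** Section 7.1.2 (QTc) and Section 7.1.3 (pregnancy) say that the participant will be withdrawn from treatment. Table 4 orders permanent discontinuation for Grade ≥ 3 retinal vein occlusion, symptomatic heart failure, and an LVEF fall of more than 20%. The liver lead sentence is softer than all of these.

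**6. What about INR?** The evidence is thinner. Footnote 1 does not mention INR, and neither does the entry criterion of the monitoring table. INR is nevertheless a listed stopping criterion, and both sections give it the same possible Hy's Law status as bilirubin.

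**The case against.** The strongest reply is that 7.1.1 should not be read one sentence at a time. It is headed as stopping criteria and makes Appendix 5 compulsory reading. Complying with 7.1.1 therefore includes consulting an appendix that treats the case as a stop. Section 8 also requires immediate safety concerns to be discussed with the sponsor or medical monitor, and an SAE report is due. Unnoticed continued dosing is unlikely.

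Much of this stands. A reader might infer that a site could go on dosing a possible Hy's Law case and be fully compliant. The documents do not support that, because the compulsory reference leads to text pointing the other way. They support something narrower: the two sections disagree, and the Section 8 discussion is itself about whether to continue or stop, so it does not replace a rule.

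The second reply is that the deciding text may be in what cannot be read. Figure 1's boxes are missing from the text available. The action column of Appendix 5 is damaged, though fragments mention permanent discontinuation and a bar on rechallenge. Both may be firmer than the lead sentence. This limits the finding but does not remove it, because a firmer figure would contradict the sentence that introduces it.

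Three further inferences should be resisted:

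- **Footnote 1 rarely matters.** The central panel includes "Total and Direct BIL", so fractionation may seem always to be available. The footnote's condition is immediate availability, however, and Section 10.2 itself foresees central results arriving too late for a treatment decision.
- **Confirmed cases are treated more leniently than unfractionated ones, or all six criteria are in conflict.** The unreadable parts prevent either conclusion.
- **Section 7.1 leaves severe laboratory abnormalities to the investigator.** The grammar of that list item is uncertain, and nothing here rests on it.

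**Conclusion.** The concern holds as an inconsistency of instruction. For ALT ≥ 3 × ULN with bilirubin ≥ 2 × ULN (> 35% direct), 7.1.1 is discretionary where Appendix 5 treats the event as a stop, and the labels suggested and required are both applied to the liver actions.

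The extent is one of the six Appendix 5 criteria on readable text, with INR added because of its shared Hy's Law status. Nothing is claimed about the other four. The documents give no expected rate of such cases. None is needed, since the question is which instruction applies when a case occurs.

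The conclusion assumes that the lead sentence governs Figure 1, as its wording says. If the intact figure orders discontinuation, the conflict lies within 7.1.1 itself and the same edit resolves it. The change should be made, because it gives a clear stop for a serious safety event at little cost. Confidence is medium because of the unreadable parts.

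**What to change.** 1. State in 7.1.1 that study treatment will be discontinued when ALT ≥ 3 × ULN occurs with either:
   - bilirubin ≥ 2 × ULN, with > 35% direct or with fractionation not immediately available; or
   - INR > 1.5, not applicable to participants on anticoagulants.
2. Keep the discretionary wording in 7.1.1 only for other liver abnormalities. While editing, check the sentence against the intact Figure 1 and the Appendix 5 action column so that all three agree.
3. Use one label for the liver actions in 7.1.1, the title of Appendix 5, and Table 11, footnote 2.

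The cost is protocol wording and slightly less investigator discretion in possible Hy's Law cases. Thresholds, visits, laboratory tests and analyses do not change.
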